#### Definition of an adverse event

In this study an adverse event (AE) will be defined based on FDA CFR Title 21: "Adverse event means any untoward medical occurrence associated with the use of a drug in humans, whether or not considered drug related" [28]. Therefore an AE is considered as any unplanned medical occurrence that affects subject's health and/or well-

being. The adverse event need not be directly related to the study device or procedure. As such, an adverse event may include any unintended outcome such as a symptom or a new diagnosis or worsening or improvement of existing medical condition.

Serious adverse event (SAE) is defined according to FDA CFR title 21: "Serious adverse event or serious suspected adverse reaction. An adverse event or suspected adverse reaction is considered "serious" if, in the view of either the investigator or sponsor, it results in any of the following outcomes: Death, a life-threatening adverse event, inpatient hospitalization or prolongation of existing hospitalization, a persistent or significant incapacity or substantial disruption of the ability to conduct normal life functions, or a congenital anomaly/birth defect. Important medical events that may not result in death, be life-threatening, or require hospitalization may be considered serious when, based upon appropriate medical judgment, they may jeopardize the patient or subject and may require medical or surgical intervention to prevent one of the outcomes listed in this definition. Examples of such medical events include allergic bronchospasm requiring intensive treatment in an emergency room or at home, blood dyscrasias or convulsions that do not result in inpatient hospitalization, or the development of drug dependency or drug abuse".

A SAE is therefore an AE that:

- 1. Results in death.
- 2. Is life-threatening at the time of the AE.
- 3. Results in an inpatient hospitalization or prolongation of existing hospitalization.
- 4. Results in a persistent or significant incapacity or substantial disruption of the ability to conduct normal life functions.
- 5. Is a congenital anomaly/birth defect.
- 6. May require medical or surgical intervention to prevent one of the outcomes listed above.

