# 12) Adverse events

Collecting Adverse Events

Study staff and PI are responsible for soliciting, recording and reporting any adverse event during the study period. In addition to unsolicited reports by subjects, the PI and study staff will open every visit by asking for any change in health or any other complaint since the last visit.

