#### Documenting and reporting adverse events

All adverse events need to be recorded and reported to the local IRB and the sponsor in a timely manner and in accordance to local regulations.

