#### Assessment of advance event causality

For each AE the PI is responsible for assessing the relationship between study procedure including application of study device and the AE in order to determine causality. The relationship of AE to study activities will be recorded in the AE log. The PI will use the following terms to describe relationship of AE to study activities:

Probable: the AE appears to follow a temporal sequence following study related activities, or has a dose relationship with study activities (i.e. worse when activity increased and visa versa) and cannot be attributed to other causes such as past medical history.

Possible: the AE appears to follow a temporal sequence following study related activities, or has a dose relationship with study activities (i.e. worse when activity increased and visa versa) but could be attributed to other causes such as past medical history and other therapies.

Unlikely: the AE does not appears to follow a temporal sequence following study related activities, and does not demonstrate a dose relationship with study activities (i.e. worse when activity increased and visa versa) and could reasonably be attributed to other causes such as past medical history and other therapies.

Cannot assess: the PI cannot make determination of causality at this time due to insufficient information and/or contradictory or unreliable information. The PI will frequently re-evaluate the AE in order to classify it into one of the classes above.

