# 15) Potential Benefits to Subjects\*

Regardless of the research outcomes, the patients will benefit from immediate symptom relief. They will also have better healing of the lesions. They may also experience no recurrence in the areas treated. If our hypothesis is correct, they will be spared worsening of disease. Given the poor overall management of HS nationwide, patients will benefit from

care at an expert medical center. Patients will also have access to free dressing and wound care for the duration of the study which are infrequently covered for HS.

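### The working definition of an adverse event drops the requirement that the event be untoward and admits improvement of an existing condition (minor wording correction)

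*Protocol*

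**What the plan says.** Under *Definition of an adverse event*, section 12 of the protocol first quotes the regulation: "Adverse event means any untoward medical occurrence associated with the use of a drug in humans, whether or not considered drug related". It then derives its own working form, in which an AE is "any unplanned medical occurrence that affects subject's health" or well-being, and illustrates it: "an adverse event may include any unintended outcome such as a symptom or a new diagnosis or worsening or improvement of existing medical condition".

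The rest of section 12 applies this definition. On collection, the PI and study staff "will open every visit by asking for any change in health or any other complaint since the last visit". On reporting, "All adverse events need to be recorded and reported to the local IRB and the sponsor". On causality, the PI rates the relationship of each AE to study activities as probable, possible, unlikely or cannot assess.

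**The concern.** The source definition and the restatement point in different directions. *Untoward* means unfavourable. *Unplanned* and *unintended* say only that the event was not foreseen or sought, and they apply to good changes as well as bad ones. The example removes any doubt by placing improvement next to worsening.

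An AE log is meant to describe harm. If it may also hold favourable changes, the number of AEs and the share of subjects with an AE become a mixture, and two recorders can classify the same favourable change differently. The study describes no control group, so there is no comparator rate against which an inflated count would stand out. An improvement in the log would also carry a causality rating, so a favourable change that followed the gel in time, with no other explanation, could appear as an AE probably related to study activities.

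**Working it through.** The protocol states no figure to reproduce. The check is mainly a comparison of its texts.

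**1. Source against restatement (section 12, *Definition of an adverse event*).**

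| Step in the text | Test applied | Direction |
|---|---|---|
| Regulation as quoted | untoward | harm only |
| First restatement | unplanned | none |
| Worked example | unintended; improvement listed | either way, explicitly |

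Each step is presented as following from the one before, but the restriction to harm is lost at the second step and reversed at the third. No other part of the protocol withdraws or narrows the mention of improvement.

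**2. Does the wording reach the AE log?**

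- *Collection:* the opening question at each visit asks about any change in health, so it picks up favourable changes too.
- *Recording and reporting:* the duty covers all AEs. The sentence asks for timeliness and compliance with local regulations, but it states no filter by direction or severity.
- *Causality:* every AE is rated. The dose criterion, "has a dose relationship with study activities (i.e. worse when activity increased and visa versa", is illustrated only with harm and does not fit an improvement. The temporal criterion does fit one.

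So an improvement classed as an AE passes through every later step with nothing to remove it.

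**3. Which improvements are caught?** The example is limited to unintended outcomes. Section 15 expects benefit ("the patients will benefit from immediate symptom relief") and better healing of the lesions, so improvement of the treated tunnel can be argued to be intended and therefore outside the sentence. Unplanned improvement of an untreated lesion or of another disease is inside. The protocol does not say where intended benefit ends.

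**4. What is not touched.**

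- An improvement does not by itself meet any of the six serious AE criteria in section 12.
- The pause rule in section 11 rests on death, on admission for an AE at the treatment site, or on a serious AE directly related to the study procedure.
- The events that section 11 names for review in the CRF are all harms.
- The primary endpoint in section 7 is a bacterial count by quantitative PCR.

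**5. Scale.** Inputs: 12 planned completers and up to 15 consented (section 22; section 4 also gives 15). Let *k* be the number of subjects whose *only* logged AE is an improvement, and *N* the denominator. The share of subjects with an AE then rises by *k*/*N*. For *k* = 1:

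- *N* = 15: 1/15 = 0.067, or 6.7 percentage points.
- *N* = 12: 1/12 = 0.083, or 8.3 percentage points.

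A subject who already has another AE contributes 0 to this share. The protocol gives no basis for the value of *k*, which may be zero.

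**The case against.** The strongest defence is that the passage should be read as a whole. The protocol says that its definition is based on the regulation, so *untoward* can be taken as controlling. The example is permissive and merely illustrates. *Unintended* already removes the most likely improvement, that of the treated tunnel, and what remains must arise within a four-week study. With at most 15 subjects and a log that is rated entry by entry, an entry describing an improvement would be easy to see and set aside. The wording errs towards recording too much and hides no harm.

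Most of this stands as a limit on the consequence. It does not remove the error. A permissive example still authorises the entry, and once an entry is classed as an AE the reporting duty covers it. That such entries can be set aside later means that someone must review and reclassify them, and the protocol gives no rule for doing so.

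A reader might infer more than the text supports:

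- *Every response to treatment becomes an AE.* The restriction to unintended outcomes arguably excludes the benefit sought in the treated tunnel.
- *The safety summary cannot be interpreted.* The events named for review in section 11 are unaffected. Section 7 lists no AE proportion as an endpoint, and mixed entries can be separated on review.
- *The AE proportion is inflated by a large, known amount.* The protocol gives no rate of unintended improvement. Any such subject must also have no other AE, yet each subject undergoes punch incisions at the first visit, and section 14 lists pain and bleeding among the procedural risks.

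**Conclusion.** The point holds as a minor inconsistency. The working definition is wrong when measured against the definition that it claims to follow, and its wording allows unintended improvements to be logged, rated and reported as AEs. The practical effect is confined to raw AE counts, reporting and causality entries, which cannot be read purely as harm without review of each entry.

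The size is 6.7 to 8.3 percentage points on the share of subjects with an AE for each subject whose sole logged AE is an improvement, and otherwise nothing. This assumes that such a share is reported at all; the protocol does not name it as an endpoint, and a SAP was not available to check. The conclusion on the text itself needs no assumption about how often such improvements occur.

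**What to change.** Make three small changes under *Definition of an adverse event* in section 12:

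1. Delete the words *or improvement* from the example, leaving worsening of an existing condition.
2. In the restatement, replace *unplanned* with *untoward* (or *unfavourable*).
3. In the example, add the same qualifier to *unintended outcome*.

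The first change alone is not enough, because an unplanned improvement would still satisfy the two directionless phrases that remain.

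Nothing is lost from safety reporting, since unfavourable symptoms, new diagnoses and worsening all stay in. Improvement in the subject's HS is still captured by outcomes already collected under section 7: HS-PGA, pain VAS, erythema, exudate and quality of life. The cost is a few words in an amendment, with no effect on sample size, visits or the primary endpoint.

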#### Documenting and reporting adverse events

All adverse events need to be recorded and reported to the local IRB and the sponsor in a timely manner and in accordance to local regulations.

#### Assessment of advance event causality

For each AE the PI is responsible for assessing the relationship between study procedure including application of study device and the AE in order to determine causality. The relationship of AE to study activities will be recorded in the AE log. The PI will use the following terms to describe relationship of AE to study activities:

Probable: the AE appears to follow a temporal sequence following study related activities, or has a dose relationship with study activities (i.e. worse when activity increased and visa versa) and cannot be attributed to other causes such as past medical history.

Possible: the AE appears to follow a temporal sequence following study related activities, or has a dose relationship with study activities (i.e. worse when activity increased and visa versa) but could be attributed to other causes such as past medical history and other therapies.

Unlikely: the AE does not appears to follow a temporal sequence following study related activities, and does not demonstrate a dose relationship with study activities (i.e. worse when activity increased and visa versa) and could reasonably be attributed to other causes such as past medical history and other therapies.

Cannot assess: the PI cannot make determination of causality at this time due to insufficient information and/or contradictory or unreliable information. The PI will frequently re-evaluate the AE in order to classify it into one of the classes above.

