# 8) Procedures Involved\*

After informed consent is obtained from each subject, they will be invited to participate in the study for 3 visits over 4 weeks. The procedures involved are listed in the table of assessments.

Week	0	+2	+4
Visit	V1	V2	V4
Window (days)	0	±3	±3
Informed consent	X		
Eligibility	X		
Subject ID assignment	X		
Chart review	X		
Demographics	X		
HS history	X		
Medical history	X		
Concomitant medication	X	X	X
Physical exam (focused)	X	X	X
HS lesion map	X X X X	X X X	X
HS lesion ultrasound	X	X	X X X
Hurley stage	X	X	X
HS-PGA	X	X	X
Pain (VAS) -General	X	X	X
Pain (VAS) -target TW	X	X	X
Pain medication usage	X	X	X
past 3 days		Λ	Λ
Height	X		
Body weight	X		X
Exudate	X	X X	X
Erythema	X	X	X
Range of motion affected joint	X	X	X
Incision and drainage	X		
Product application	X	X	X
Tissue collection	X		X
Serum collection	X		X X
QOL	X		X
Work/school days lost	X	X	X
Number of dressing used	X	X	X
Photography	X	X	X
Ease of ABWG	i		
application	X	X	X
Adverse events	X	X	X

At the first visit, the medical history will be reviewed and demographics, HS history and concomitant medications will recorded using the medical chart and history given by the patient. Then, the tunnel of interest will be identified and a picture of the lesion will be taken. The first swab of the lesion will be performed and placed in a collection tube labeled with the patient number, date and "pre." The area will be cleaned, then anesthetized using local anesthesia. Once the area is properly anesthetized, a punch incision will be made and the tissue placed in a sterile petri dish lined with gauze labeled with the patient number, date and 1. After the tissue is place in the dish, sterile PBS will be added to the gauze.

A probe will then be inserted into the tunnel to identify the terminal end. A second punch incision will be made at the end of the tunnel and the tissue will be collected in a second sterile petri dish labeled with the patient number, date and 2. Hemostasis will be achieved. Once hemostasis is achieved, a second picture will be taken of the lesion. The ABWG (BlastX, NextScience, Jacksonville, FL) will then be applied to both punch sites using a tongue depressor. Absorbent dressing will be applied to cover the wound.

In the days between visits, patients will apply one fingertip unit of the ABWG to the study wound daily.

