#### 14) Risks to Subjects\*

The procedures involved in the study are within the standard care for people with HS and are indicated. Therefore, the main added risk we anticipate is unintentional reveal of PHI.

Additional risks that are inherent in the standard care treatment include: pain, bleeding, infection and abnormal scarring that are related to the surgical procedures. There are minimal risks associated with the FDA cleared ABWG that include stinging or burning at the application site.

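### The single causality rating combines the surgical procedure and the gel, and home gel use is not recorded, so for local events either could cause the AE log cannot separate the two

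*Protocol*

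**What the plan says.** **Causality rating.** Section 12 (Assessment of advance event causality) gives the PI one task per AE: "assessing the relationship between study procedure including application of study device and the AE in order to determine causality". The record follows the same form: "The relationship of AE to study activities will be recorded in the AE log". No separate rating for the gel is described.

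**The scale.** Probable and Possible both start from the same condition: "the AE appears to follow a temporal sequence following study related activities, or has a dose relationship with study activities". They differ in whether another cause could explain the event. Unlikely requires that there is no temporal sequence, "and does not demonstrate a dose relationship with study activities", and that another cause is reasonable. Cannot assess covers insufficient or contradictory information, with re-evaluation.

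**Risks.** Section 14 keeps the two sources apart. It attributes pain, bleeding, infection and abnormal scarring to the surgical procedures. For the gel it says: "There are minimal risks associated with the FDA cleared ABWG that include stinging or burning at the application site".

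**Exposure.** Section 8 describes two punch incisions at the first visit, then: "The ABWG (BlastX, NextScience, Jacksonville, FL) will then be applied to both punch sites using a tongue depressor". After that: "In the days between visits, patients will apply one fingertip unit of the ABWG to the study wound daily". The table of assessments lists product application and ease of application at all three visits. It has no diary, application count, missed-day or returned-product item.

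**The concern.** The protocol distinguishes the two sources of harm when it describes risk and merges them when it records harm. Section 30 calls the gel the main study intervention, and all subjects receive both the punches and the gel, so no comparison group can help to tell the two apart. The PI's judgment at the time of the event is the only attribution the study will have, and the plan asks for it in a form that does not say which exposure is suspected.

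The missing home-use record adds to this. The scale asks whether an event worsens with more of an activity and eases with less. The punches are single procedures at a visit. The exposure that recurs daily, and could be skipped or paused, is the gel at home. Without a record of use, that question rests on the subject's memory. The same gap means that a small or absent change in bacterial load at 4 weeks could reflect an ineffective gel or a gel that was not applied.

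Neither gap can be repaired at analysis: a rating never made and use never recorded cannot be recovered.

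**Working it through.** No sample size, power or error rate is involved, and the plan states no figure to reproduce. The check sets the passages side by side and counts applications.

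**1. Can timing separate the two sources?** The gel goes onto both punch sites at the visit at which they are made, and continues daily. A local event after the first visit therefore follows both the procedure and a recent gel application. The temporal criterion is met by both at once, and a rating against study activities as a whole does not show which was suspected.

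**2. Can the event term separate them?**

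| Event | Protocol links it to | Separable by term? |
|---|---|---|
| Stinging or burning on application | Gel (Sections 11 and 14) | Yes |
| Pain or discomfort at the site | Pain to surgery (Section 14); discomfort from product application (Section 11) | Only if the report ties it to application |
| Infection, bleeding | Surgery (Section 14) | No, if the gel is also suspected |
| Delayed healing at the punch sites | Not listed | No |

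That the gel might be suspected in the last two rows is an assumption. The protocol does not list those events as gel risks, but the gel is placed on the same open sites.

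**3. Where does dose relationship enter the scale?** For Probable and Possible it is joined to timing by *or*, so timing alone is enough. For Unlikely it is joined by *and*, so the PI must judge it absent. It therefore has to be judged for Unlikely and is optional for the other two.

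**4. How much gel use goes unrecorded?** Inputs: visits at weeks 0, 2 and 4 (Section 8 table), final visit at day 28 ± 3 (Section 6), daily use between visits (Section 8), 12 completers and up to 15 consented (Section 22).

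For a final visit on day D, scheduled application days run from 0 to D, which is D + 1 days. Three are visit days, leaving D − 2 home days.

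| Final visit | Home / all | Share |
|---|---|---|
| Day 25 | 23 / 26 | 88% |
| Day 28 | 26 / 29 | 90% |
| Day 31 | 29 / 32 | 91% |

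At day 28, over all subjects: 12 × 26 = 312 and 15 × 26 = 390 home applications.

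**5. How long is the recall?** The nominal gap between the second and final visits is 28 − 14 = 14 days. The longest the windows allow is 31 − 11 = 20 days.

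**6. Is use captured elsewhere?** Section 3 excludes subjects who, in the PI's opinion, cannot comply with home application; that is a judgment at entry. Section 13 names compliance as a ground for withdrawal without a measure of it. Its part on withdrawal of consent has the CRF state whether a subject withdraws only from further treatment, so formal stopping is recorded. Missed days and short pauses are not.

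**The case against.** A reader might infer more than the text supports, and four stronger readings should be set aside.

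- *The scale needs a dose relationship.* It does not. Probable and Possible can rest on timing alone, and Cannot assess is available where information is lacking.
- *The study cannot report any gel-related harm, or every local AE is affected.* Section 11 names burning or discomfort from product application for CRF review, and Section 14 lists the gel's expected reactions separately. Those events can be found by term.
- *Procedure harms are charged to the gel, or gel harms are explained away as procedural.* A combined rating does neither. An event from either source still counts as related; the rating only fails to say which source.
- *Stopping the gel goes unrecorded.* Formal discontinuation is to be explained in the CRF.

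The opposing case goes further. No decision in the protocol depends on the split: the pause rule in Section 11 turns on the treatment site or on relation to the study procedure, and device-related AE rates are not an endpoint. The study is small, unblinded and at one site, and the product is FDA-cleared and used per label. Two ratings by the same PI would often be guesses for just the events at issue. Recall of 20 days is the extreme of two visit windows, and subjects may report events between visits.

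These points stand and limit the weight of the finding. They do not remove it. The overlapping events remain unseparated, and the missing exposure record also affects the reading of the primary endpoint.

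**Conclusion.** The point holds in a limited form. For local events that either source could cause, the AE log as described cannot separate suspected gel-related from procedure-related harm. The dose-relationship criterion, optional for Probable and Possible but to be judged absent for Unlikely, cannot be checked for the gel from planned data. Actual exposure to the main intervention is also unknown when the 4-week bacterial enumeration is interpreted.

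About 90% of scheduled applications (88% to 91% across the final-visit window) have no planned record of being made or missed. How many AEs are affected cannot be calculated, because the protocol gives no expected event rates.

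The conclusion assumes one application per day, counts the three visit-day applications as observed, and takes the protocol as complete on these items. The CRF and AE log are not shown and could contain more fields, but nothing in the protocol requires them. This is a worthwhile, inexpensive improvement and does not call the study's validity or safety oversight into question.

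**What to change.** 1. **Section 12, causality.** Require two relationships for each AE, each on the existing four terms: (a) to the punch, probe or incision procedure, and (b) to the gel. In the definitions, replace the general reference to study activities with the exposure being rated. Report AEs by each relationship.
2. **Section 8, table of assessments.** Add a row for home gel use at the week 2 and final visits, taken from a daily tick sheet showing days applied, missed or interrupted. Use it for the dose-relationship criterion in rating (b), and summarise it alongside the primary endpoint.

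The cost is one extra column in the AE log and a one-page sheet for each of 12 to 15 subjects. No visit, procedure, dose or clinical rule changes. The sheet is self-reported and will contain some error. In a single-arm study, two ratings make the PI's suspicion explicit without proving the cause.
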